6.5 Time and Events Schedule

	Screening	Baseline	Day 0	Inpatient	30 d (\pm 14d) FU	12 mo (\pm 4 wk) (transcatheter)
Baseline informed consent:		X				
Multidisciplinary heart team eligibility determination		X				

	Screening	Baseline	Inpatient	Day 0	30 d (± 14 d) FU	12 mo (± 4 wk) (range) ELL
Baseline clinical assessment		X				
NYHA Classification		X				X
Blood tests: CBC, Platelet, Haptoglobin, Liver panel, Chemistry Panel, Albumin, LDH, BNP/Pro-BNP, Troponin that are obtained for medical care are captured for research. Pregnancy test if applicable before day 0 and before research CT		X	X		X	X
Vital signs and in-person visit		X			X	X
Cardiac CT contrast-enhanced gated dynamic	Screening or baseline	Screening or baseline	Inpatient or 30D		Inpatient or 30D	
BASILICA assisted TAVR Enrollment begins once attempted			X			
Echocardiogram, surface or transesophageal	Screening or baseline	Screening or baseline	X		X	X
Adverse event assessment			X X		X	X
Data capture from TVT-registry surveillance: KCCQ-12, baseline-only frailty		X			X	X

Subjects would receive continuing care from their primary physicians with consultant input as requested from the structural heart disease program.

For subjects who die, necropsy evaluation is requested to examine the heart at NIH.

6.6 Visit Schedule

[figure not shown]
All activities except TAVR/BASILICA, Consent, KCCQ, and Adverse event assessment are performed for standard clinical care.

Timing	Event
Screening (any time)	Medical, Surgical and Interventional Assessment, determination and documentation that the subject has no other options for TAVR
Screening (any time)	Cardiac CT contrast enhanced, gated dynamic
Screening (any time)	Echocardiogram, transesophageal or surface
Screening (any time)	Multidisciplinary heart team eligibility determination and documentation
Baseline (within 30 days of procedure)	Research Informed Consent to include documented Inclusion and Exclusion criteria

Baseline (within 30 days of procedure)	
Clinical Assessment to include:
 
 • Vital signs • Baseline symptoms • NYHA Classification • Other co-morbidities that could preclude the subject living the required 12 months post procedure • Surface echocardiogram-transthoracic and/or transesophageal • TVTRegistry quality surveillance data, including QOL, Frailty 
Clinical Blood tests if obtained are captured for research
 
 • CBC • Platelets • Haptoglobin • Liver Function panel • Chemistry panel • Troponin • Albumin • LDH • BNP/Pro-BNP • Pregnancy test if applicable
Day 0	
TAVR with BASILICA procedure attempted, which marks enrollment.
 
Subjects who do not proceed to BASILICA attempts are recorded as screen failures, and the reason is recorded.

Pre-discharge	
Clinical Evaluation to include:
 
 • Cardiac CT scan contrast enhance, gated dynamic- if not clinically suitable then re-schedule for 30 Day follow up visit • Surface echocardiogram and/or transesophageal • Adverse Event Assessment 
Clinical Blood tests if obtained are captured for research
 
 • CBC • Platelets • Haptoglobin • Liver Function panel • Chemistry panel • Troponin • Albumin • LDH • BNP/Pro-BNP 
Pregnancy test if applicable

30-day (± 14 days)	
Clinic/office visit to update subject's vital status to include:
 
 • Vital signs • ECG • Medication Assessment • NYHA Classification • Surface Echocardiogram and/or transesophageal • Cardiac CT scan contrast enhanced, gated dynamic if not conducted pre-discharge for clinical reasons • Clinical blood work is captured for research including: 
 CBC with platelets Haptoglobin Chemistry Panel PT INR BNP/Pro-BNP • TVTRegistry quality surveillance data, including QOL • Adverse Event Assessment
12 month (± 30 days)	
Clinic/office visit to update subject's vital status to include:
 
 • Vital signs • Medication Assessment • NYHA Classification • Surface Echocardiogram and/or transesophageal • Clinical blood work is captured for research including: 
 CBC with platelets Haptoglobin Chemistry Panel PT INR BNP/Pro-BNP • TVTRegistry quality surveillance data, including QOL • Adverse Event Assessment

6.7 Milestones

This section is submitted to comply with recent NIH IRP initiatives. Should a milestone not be met, all milestones will be shifted in time until the protocol is complete within the predicted protocol completion timeline.

- Milestone one: Regulatory phase

Regulatory approval including scientific and ethics review, at NIH and at participating sites, and FDA review, is expected to be complete by October 1 2017.

- Milestone two: Contracting phase

NIH contracts for services including clinical events adjudication are expected to be complete by October 1 2017.

- Milestone three: Site initiation

Site selection, training, and initiation is expected to be complete before November 1 2017.

- Milestone four: Enrollment

First patient should be enrolled 30 days from the initiation of the first site. Should this not occur, then the 30 day period will be extended. Enrollment should be completed within 12 months. We expect the tempo of enrollment to increase over time as additional sites and experience accrue.

Continuing reviews to IRB, DSMB, and FDA will be performed during this period.

- Milestone five: Follow-up and reporting

After the last patient is enrolled, follow-up is performed for 12 months. The study phase is changed from recruitment to follow-up and to analysis, as appropriate. We expect the primary manuscript to be prepared based on data from 30 day follow-up. We expect the final analysis to be complete within 12 months after follow-up is complete.

7.0 ELIGIBILITY ASSESSMENT

7.1 Inclusion Criteria

- Adults age \geq 21 years
- High or extreme risk of surgical aortic valve replacement according to the local multidisciplinary heart team
- Undergoing TAVR for valve-in-valve or native aortic valve failure (“on-label” TAVR)
- Deemed likely to suffer coronary artery obstruction from TAVR according to multidisciplinary heart team
- Concurrence of the study eligibility committee

7.2 Exclusion criteria

- Subjects unable to consent to participate, unless the subject has a legally authorized representative
- Excessive target aortic leaflet calcification or masses on baseline CT
- Survival despite successful procedure expected < 12 months
- Planned concurrent valve intervention in the same setting (such as transcatheter mitral valve therapy or paravalvular leak therapy)
- Subjects unwilling to participate or unwilling to return for study follow-up activities.
- Pregnancy or intent to become pregnant prior to completion of all protocol follow-up procedures

7.3 Rationale for selection criteria

The selection criteria allow enrollment of the intended population with little anticipated selection bias. Instead of functional or geometric selection criteria, the study will enroll all subjects deemed otherwise suitable for TAVR yet at risk of the problem to be addressed by BASILICA, the investigational procedure.

There are no validated prediction models for coronary artery obstruction. Features predictive of coronary obstruction will be specifically outlined to the heart team and to the study eligibility committee and captured in the data collection form.

Subjects are eligible if BASILICA laceration is contemplated for one or for two threatened coronary arteries.

The inclusive selection criteria and geographic extent of enrolling sites are expected to allow recruitment of a diverse economic, ethnic, and racial mix of patients that reflects the incident disease.

Composition of the study eligibility committee is described in section 14.10.

8.0 Strategies for Recruitment

Subjects will be recruited from the Structural Heart Disease clinical programs of the participating hospitals.

The distribution of planned enrolling sites assures accessibility of the trial to ethnically, racially, and economically diverse populations. The study will track sex, age, ethnicity, and racial background of subjects.

Once recruited, subject retention rate is expected to be high because follow-up activities are not onerous and are timed to correspond with routine follow-up medical care, without prohibitively expensive follow-up testing.

During the early clinical development of the BASILICA procedure, 3 clinical patients were treated in one week at two centers, which suggests the recruitment objectives will be met.

9.0 SAMPLE COLLECTION, STORAGE AND TRACKING PLAN

Imaging data (from angiography, CT, and echocardiography) constitute the only specimens to be collected. CT examinations performed for clinical evaluation prior to signing informed consent may be used as the baseline scan.

CT and fluoroscopy data will be analyzed at the NHLBI DIR Core Laboratory. These data will be transmitted on electronic media such as a DVD via carrier or using secure file transfer mechanisms abiding FISMA, HIPAA and local institutional standards (such as SFTP or <https://secureemail.nih.gov>).

Imaging data are transmitted to a central facility (NHLBI) using secure HIPAA compliant methods and are stored in a secure Picture Archive Computer System (PACS), according to local institutional standards.

Necropsy specimens will be handled according to local institutional medical standards and will be disposed accordingly.

10.0 BIOSTATISTICAL AND ANALYTICAL CONSIDERATIONS

10.1 Sample Size

The sample size is not statistically derived. This is a safety and feasibility study that enables patient access to a novel medical procedure, when these patients have no other good medical options to treat symptomatic aortic valve failure.

Up to 60 subjects will be consented until 30 subjects undergo attempted BASILICA TAVR in this protocol.

10.2 Study Analysis

Clinical events are classified by the local site Principal Investigator and confirmed by the NIH Principal Investigator. The results of the study will be released within 12 months of study completion.

Primary and secondary analyses will be stratified according to the setting for TAVR, whether native or bioprosthetic, and whether the bioprosthetic valve will intentionally be over-expanded to achieve a greater than nominal orifice area.

The study will be analyzed using descriptive statistics, including a case-by-case narrative summary of major adverse events. Kaplan-Meier estimates will be used to estimate the overall survival and the event-free survival. Afterwards, we will survey for parameters associated with an increased risk of major adverse events by exploratory subgroup analysis and regression models.

10.2.1 Primary efficacy endpoint

The primary endpoint is Clinical success (measured at exit from the catheterization laboratory). All of the following must be present:

- Successful BASILICA traversal and laceration of the intended aortic leaflet; and
- Absence of procedural mortality; and
- Successful access, delivery, and retrieval of the BASILICA device system; and
- Successful TAVR device implantation; and
- Absence of acute life-threatening ostial coronary artery obstruction (by immediate hemodynamics, by angiography, and by iFR <0.89 if obtained)
- Freedom from emergency cardiac surgery or reintervention related to the BASILICA TAVR procedure, including attempted implantation of coronary artery stents to treat TAVR-induced coronary artery obstruction.

Additional details about primary endpoint

Valve post-dilatation is not considered unplanned re-intervention. When pre-positioned coronary artery stents are not able to be retrieved, they may be implanted without impacting the primary endpoint.

10.2.2 Primary safety endpoint

The primary safety endpoint is freedom from major adverse clinical events (MACE) according to VARC-2 at 30days.

10.2.3 Secondary Endpoints

Secondary endpoints include

- Technical success, defined as clinical success irrespective of coronary artery stenting
- Clinical success without stroke, as determined by site physicians
- Technical success of BASILICA only (delivery and removal of BASILICA catheter equipment, traversal, and laceration of intended aortic leaflet)
- Coronary artery obstruction measured as instantaneous wave-free pressure ratio (iFR) or related measurements using a solid-state pressure-transducer guidewire, if measured
- Survival to discharge, to 30d, and to 12mo
- Neurological events as reported by the site clinicians
- Access and vascular complications
- Peri-procedural and spontaneous acute myocardial infarction
- Pericardial effusion or tamponade
- VARC-2 bleeding complications
- AKIN acute kidney injury
- Freedom from hemolytic anemia related to BASILICA TAVR
- BASILICA Device or Procedure related technical failure: acute embolism, mitral valve injury, traversal into left atrium, coronary artery injury induced by BASILICA, etc.
- Rotational orientation of transcatheter heart valve commissures with regard to coronary artery ostia

- Hemodynamic instability caused by BASILICA before TAVR
- TAVR thrombosis on CT or echocardiography during follow-up
- Endocarditis during follow-up
- Outcomes for laceration of native versus surgical aortic valves, for single versus double scallop laceration, and for procedures with versus without bioprostheses intentional overexpansion

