6.4 BASILICA TAVR Procedure

The BASILICA TAVR procedure is planned from a contrast-enhanced CT of the heart to select a suitable transcatheter heart valve size, predict suitability of the sub- and supra-annular landing zone, and predict post-TAVR coronary obstruction related leaflet encroachment on the sinotubular junction and coronary artery ostia. Knowledge of the aortic valve operative history is integrated into this assessment. These data are used to select a BASILICA traversal point, radiographic landmarks, and fluoroscopic projection angles.

The procedure is performed under general anesthesia or under moderate sedation at the discretion of the institutional heart team. The BASILICA procedure has three steps: (1) leaflet traversal with a guidewire, followed by (2) leaflet laceration, immediately followed by (3) TAVR. These are all guided by fluoroscopy and adjunctive echocardiography as needed.

Research study participation is defined as beginning the moment BASILICA traversal is attempted.

First catheter access is obtained typically via four arterial introducer sheaths (two for BASILICA, one for hemodynamics and angiography, and one for TAVR) and at least one venous introducer sheaths for temporary transvenous pacing. Anticoagulation with heparin or equivalent achieves an activated clotting time > 300s.

Hemodynamic and echocardiography measurements are recorded at baseline including gradients across the aortic valve, severity of valvular obstruction and severity of valvular regurgitation.

Two retrograde catheters are positioned, using a guidewire anchor as needed, in the LVOT and Aorta respectively. Care is taken to avoid entrapment of mitral valvular structures. A snare catheter is positioned in the LVOT. A coaxial traversal guiding catheter system (typically tandem catheters) directs electrosurgery devices (typically a rigid 0.014" guidewire inside a polymer jacket wire convertor) against the base of the coronary cusp targeted for laceration, using fluoroscopic and/or echocardiographic guidance.

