Hemodynamics are recorded quickly after laceration before TAVR. Coronary artery stent systems are positioned prophylactically at the discretion of the operator. Predilatation, including intentional disruption of the bioprosthetic valve frame, is performed at operator discretion, before or after TAVR. Then TAVR is performed using established techniques typically during rapid ventricular pacing. The device size and inflation volumes are selected and applied at the discretion of the operator. Post-dilatation is performed at operator discretion to achieve an optimum TAVR result. Coronary artery patency is established using angiography and, if employed, using prepositioned pressure-tip guidewires. Coronary artery pressure (instantaneous wave-free ratio, *iFR*) may further be examined if possible at the discretion of the operator.

Completion hemodynamics and echocardiography are recorded. Finally, percutaneous femoral artery and vein vascular hemostasis is obtained and the subject convalesces in the appropriate inpatient recovery unit.

Before discharge, follow-up transthoracic echocardiography is recorded. A single contrast-enhanced CT of the heart is obtained before discharge if renal function allows, otherwise it is deferred as long as 30-days. Blood tests are recorded for research only as obtained for medical care.

Anticoagulation and antiplatelet therapy is prescribed after discharge at the physicians' discretion, and is recorded.

All subjects are to be enrolled in the TVT-Registry postmarketing TAVR registry.

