10.3 Stopping Rules and Data Safety Monitoring

A Data and Safety Monitoring Board (DSMB) appointed by the NHLBI Division of Intramural Research will monitor the safety of subjects in the study as described in the investigational plan. All members of the DSMB are unaffiliated to the study. The NHLBI DSMB will review the protocol progress report at six month intervals, or more frequently upon request of PI, IRB, and/or NHLBI Clinical Director. The DSMB may recommend early termination of the study for considerations of safety and efficacy. Unanticipated Adverse Device Effects (UADEs) will be submitted to the DSMB following the same timelines as the IRB (See section 9.2.4).

In the case of death or serious UADE, if the sponsor and the principal investigator determine that the event presents an unreasonable risk to the participating subjects, the clinical trial will be terminated within 5 working days after making that determination and not later than 15 working days after the sponsor first receives notice of the effect. [21 CFR 812.46]. All clinical sites will be notified of this action.

Each institutional IRB will review all Serious Adverse Events, Unanticipated Adverse Device Effects, and Unanticipated Problems, and may choose to suspend or terminate the protocol based on those findings. We believe this will protect subject safety.

We propose different stopping rules based on whether the operator elects intentionally to over-expand the bioprostheses.

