10.3.1 Anticipated mortality

There are few data available to guide mortality assumptions. In an international registry of valve-in-valve TAVR, the short-term (30-day) mortality of coronary obstruction complicating TAVR was 50%, despite coronary stenting {Ribeiro, 2017 #362183}. The long-term mortality is expected to be larger. There is no registry of subjects not offered valve-in-valve TAVR because of threatened coronary obstruction.

Absent data, we are forced to use judgement and experience to estimate clinically acceptable mortality for this group of patients with “no good options.” We assume that intentional fracture of surgical bioprosthetic valve frames would confer incremental mortality, although there are no available data. To come to this determination, we polled our lead site investigators, who are selected for their high-volume experience and quality. The best estimate of clinically-acceptable 30-day mortality was 15% for standalone BASILICA and 20% for BASILICA with valve fracture.

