10.3.2 Stopping Rules for no intentional overexpansion of bioprosthetic stratum

The study will be monitored to ensure that the mortality within 30-days after the procedure does not substantially exceed an anticipated rate. We anticipate the rate of 30-day mortality is 15% or less and determine the stopping rule by a Bayesian approach [8]. The stopping boundary is reached if the posterior probability that the 30-day mortality rate exceeds 15% is at least 90%. We take our prior distribution to be a beta distribution so that our prior clinical opinion is worth 20% of the weight we will place on the new study data, which gives the prior parameters $a = 0.9$, $b = 5.1$. Hence when we make decisions about stopping the study, the data from the study will dominate over the prior opinion.

The following table summarizes the threshold numbers for the stop rule boundary, which would lead to a recommendation to stop the study due to the excess 30-day mortality.

Number of subjects in the stratum	Stop if the number of deaths within 30 days reaches
2	2
3-6	3
7-11	4
12-16	5
17-21	6
22-26	7
27-30	8

We investigated the performance of the above stopping rule by a simulation study. In each simulation run, we generated a study with 30 independent Bernoulli trials, each with a true certain 30-day mortality, and compared these outcomes with the above stopping boundary to determine whether the study was stopped. We repeated the simulation 100,000 times and computed the proportion of stopped studies using the above stopping rule. The following table summarizes the performance of this stopping rule:

True 30-day mortality rate	10%	15%	20%	25%	30%	35%
Proportion of Stopped Studies	4.8%	17.3%	39%	62.3%	81.3%	92.2%
Average number of subjects	29.1	27	23.5	19.4	15.4	12.1
Average number of 30-day mortality	2.9	4	4.7	4.9	4.6	4.2

These simulation results suggest that our stopping rule has a low probability stopping a study when the true 30-day mortality rate is 15% or less, and the probability of stopping a study is high when the true 30-

day mortality rate exceeds 15%. There, we believe that our Bayesian stopping rule for 30-day mortality has satisfactory statistical properties.

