10.3.3 Stopping Rules for intentional overexpansion of bioprosthetic stratum

The study will be monitored to ensure that the mortality within 30-days after the procedure does not substantially exceed an anticipated rate. We anticipate the rate of 30-day mortality is 20% or less and determine the stopping rule by a Bayesian approach [8]. The stopping boundary is reached if the posterior probability that the 30-day mortality rate exceeds 20% is at least 90%. We take our prior distribution to be a beta distribution so that our prior clinical opinion is worth 20% of the weight we will place on the new data. This gives the prior parameters $a = 1.2$, $b = 4.8$. Hence when we make decisions about stopping the study, the data from the study will dominate over the prior opinion.

The following table summarizes the threshold numbers for the stop rule boundary, which would lead to a recommendation to stop the study due to the excess 30-day mortality.

Number of subjects in the "overexpansion of bioprosthetic stratum"	Stop if the number of deaths within 30 days reaches
3-5	3
6-8	4
9-12	5
13-16	6
17-20	7
21-24	8
25-28	9
29-30	10

We investigated the performance of the above stopping rule by a simulation study. In each simulation run, we generated a study with 30 independent Bernoulli trials, each with a true certain 30-day mortality, and compared these outcomes with the above stopping boundary to determine whether the study was stopped. We repeated the simulation 100,000 times and computed the proportion of stopped studies using the above stopping rule. The following table summarizes the performance of this stopping rule:

True 30-day mortality rate	10%	15%	20%	25%	30%	35%	40%
Proportion of Stopped Studies (%)	1.6%	6.9%	18.9%	38.3%	60.5%	78.5%	90.5%
Average number of subjects	29.6	28.7	26.7	23.6	19.7	16	12.7
Average number of 30-day mortality	3	4.3	5.3	5.9	5.9	5.6	5.1

These simulation results suggest that our stopping rule has a low probability stopping a study when the true 30-day mortality rate is 20% or less, and the probability of stopping a study is high when the true 30-day mortality rate exceeds 20%. There, we believe that our Bayesian stopping rule for 30-day mortality has satisfactory statistical properties.

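### Does the over-expansion stratum need a rule for when intention is fixed and how a changed plan is counted?

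*Combined protocol and SAP*

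**What the plan says.** The same grouping is used for two purposes.

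- **Analysis.** Section 10.2 stratifies primary and secondary analyses by native or bioprosthetic setting and by "whether the bioprosthetic valve will intentionally be over-expanded to achieve a greater than nominal orifice area". Section 10.2.3 lists among the secondary endpoints outcomes "for procedures with versus without bioprostheses intentional overexpansion".
- **Stopping.** Section 10.3 states "We propose different stopping rules based on whether the operator elects intentionally to over-expand the bioprostheses". Section 10.3.2 applies a 15% limit to the stratum without intentional over-expansion. Section 10.3.3, headed "Stopping Rules for intentional overexpansion of bioprosthetic stratum", applies a 20% limit to the other. Each table gives a number of deaths "which would lead to a recommendation to stop the study due to the excess 30-day mortality".

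The limits come from section 10.3.1, where the polled site investigators accepted "15% for standalone BASILICA and 20% for BASILICA with valve fracture".

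On timing, section 6.4 says "Research study participation is defined as beginning the moment BASILICA traversal is attempted" and, later, "Predilatation, including intentional disruption of the bioprosthetic valve frame, is performed at operator discretion, before or after TAVR".

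**The concern.** Participation starts at traversal, while the frame may be disrupted before or after the new valve goes in, at the operator's discretion. A plan can therefore change after the subject is enrolled. No section dates the intention, and none says where to count a subject whose planned over-expansion was abandoned or whose over-expansion was decided during the procedure. The wording also shifts: section 10.3.1 speaks of fracture, section 10.3.3 of intentional over-expansion.

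If membership followed what was done, events after enrolment could decide which boundary a death counts against. A subject planned for over-expansion who dies before it is performed is the obvious case. The two tables have different thresholds at most stratum sizes, so the choice could change whether the DSMB receives a recommendation to stop. For the comparison in section 10.2.3, which is descriptive, only reproducibility of the grouping is at stake.

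**Working it through.** **1. Reproduce the boundaries.** Inputs from sections 10.3.2 and 10.3.3: priors Beta(0.9, 5.1) with limit 15%, and Beta(1.2, 4.8) with limit 20%; stop at posterior probability of at least 0.90. For n subjects, the threshold is the smallest d with 1 − F(limit; a + d, b + n − d) ≥ 0.90, where F is the beta distribution function. Both printed tables reproduce at every n from 1 to 30. Exact stopping probabilities with all 30 subjects in one stratum are 17.5% at 15% mortality (plan 17.3%) and 19.2% at 20% mortality (plan 18.9%).

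**2. Where the strata differ.** The thresholds agree only at n = 3, 4, 5, 7, 8 and 12. Elsewhere from n = 2, membership matters.

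**3. Can one death change the study-level result?** Sometimes.

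| Without over-expansion | With over-expansion | Boundary reached? |
|---|---|---|
| 5/15 (posterior 0.925) | 3/15 (0.456) | Yes, first stratum |
| 4/14 (0.842) | 4/16 (0.627) | No |
| 3/10 (0.81) | 5/10 (0.95) | Yes, second stratum |
| 4/11 (0.91) | 4/9 (0.89) | Yes, first stratum |

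Rows 1 and 2 differ by one reclassified death, and the decision changes. Rows 3 and 4 also differ by one death: each stratum changes state, but the study reaches a boundary either way.

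**4. Average effect.** This is an illustration, because the documents give neither the share of subjects planned for over-expansion nor how often plans change. Simulation of 200,000 trials of 30 subjects, true mortality 15% without and 20% with over-expansion, tables checked after each subject. A share of planned-group deaths is counted as without, and no survivors are moved, which is the extreme form.

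| Planned share | 0% moved | 5% | 10% | 25% | 50% |
|---|---|---|---|---|---|
| One half | 22.6% | 22.9% | 23.5% | 26.7% | 36.1% |
| One third | 21.8% | 22.0% | 22.4% | 23.9% | 28.6% |
| One quarter | 21.1% | 21.2% | 21.3% | 22.4% | 25.3% |

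Entries are the chance of reaching either boundary. At 10% moved the largest change is 23.5 − 22.6 = 0.9 points. If survivors move at the same rate (half planned), 5/10/25/50% moved gives 23.0/23.3/24.4/26.0%. In the reverse direction (late additions, half planned, deaths only), 0/5/10% gives 22.7/22.6/22.6%.

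Single boundaries move more but partly offset. With half planned and 10% of deaths moved, the boundary without over-expansion goes from 11.4 to 15.4% and the other from 12.6 to 9.5%.

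**5. When true mortality is well above a limit.** With 40% mortality in the over-expansion stratum (half planned, deaths only), 0/5/10% moved gives 71.4/69.2/67.3%, a loss of up to 71.4 − 67.3 = 4.1 points. With 30% mortality in the other stratum and the reverse move, 61.3/59.2/57.3%, a loss of up to 4.0 points.

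**6. One death certainly moved.** Moving one randomly chosen planned-group death to the other stratum changes the either-boundary outcome in 14.8/13.0/11.4% of all simulated trials (half/third/quarter planned). Only 95.8/87.3/78.5% of trials have such a death. Among those, the proportions are 14.8/0.958 = 15.4%, 13.0/0.873 = 14.9% and 11.4/0.785 = 14.5%, so about 15% throughout. This is conditional on a move and does not say how often one occurs.

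**7. Does the text give a default?** Section 10.2 uses the future tense with intention, section 10.3 uses the operator's election, the headings of 10.3.2 and 10.3.3 say intentional, and so does 10.2.3. Under the election wording, a deliberate late over-expansion belongs to the over-expansion stratum. For an abandoned plan, intention wording favours the planned group. Table 1 in section 4.1 lists intended over-expansion or fracture as a single predictor, section 7.3 says predictive features go on the data collection form, and section 14.10 has candidates' clinical data confirmed before enrolment. A pre-procedure record is therefore likely, although the form itself is not in the documents.

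**The case for a change.** The strongest case for a change is that a formal stopping count needs a defined numerator and denominator. Intention wording without a date leaves the abandoned plan open, and no sentence links the data form to the strata. One dated item and a sentence or two would settle it without touching boundaries, sample size or care. The DSMB's freedom to recommend termination on other safety grounds (section 10.3) softens the problem but does not define the stratum.

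Much of this stands as description. The definition is missing, the shift from fracture to over-expansion is loose drafting, and a single death near a boundary can decide the outcome. Two things weigh against it. Any whole-number boundary is sensitive to one death, and nothing in the documents suggests that changed plans would be frequent. Fixing the stratum by plan is also not plainly better. Section 10.3.1 justifies the higher limit by the added mortality assumed for fracture itself, so counting by plan would hold a subject fractured after a change of plan to the 15% limit, and one planned but never fractured to the 20% limit. Counting by performance has the opposite fault, letting events after enrolment choose the group.

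**Conclusion.** The observation is accurate, but no change to the plan is needed. This is a gap in detail that the DSMB and analysts can fill from wording that already points to intention, probably with a record made before the procedure. Following the plan as written does not lead to a demonstrated wrong result.

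At the stated mortality limits, moving 5 to 10% of planned-group deaths changes the chance of reaching either boundary by less than 1 point. If one stratum's true mortality were 30% or 40%, as in the cases above, the same misclassification would cost about 2 to 4 points of stopping probability. One moved death changes the outcome in about 15% of trials that have such a death. These figures rest on assumed planned shares of a quarter to a half (a half only for the 30% and 40% cases), on assumed rates of changed plans, and on outcomes being known after each subject. Crossing a boundary produces a recommendation rather than an automatic stop, and section 10.2 already calls for case-by-case narratives of major adverse events, where a changed plan can be described. The comparison in section 10.2.3 is descriptive in a 30-subject study and carries no formal decision.
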